3.5.3 Follow-Up Visits- Prior to Disease Progression

Patients who complete trial treatment without evidence of disease progression will move into the Follow-up Phase and may be assessed every 60 days (\pm 7 days) for 6 months; then every 90 days (\pm 14 days) for 2 years; then every six months (\pm 28 days) for 2 years, then annually (\pm 6 weeks) after finishing treatment by radiologic imaging or other clinical assessments to monitor disease status. Imaging assessment will be performed at each scheduled post-treatment follow-up visit for up to 3 years. Every effort should be made to collect information regarding disease status until the start of new anti-neoplastic therapy, disease progression, death, or end of the study. If the patient cannot return to the Clinical Center for any of these visits, a request will be made to have a local physician or laboratory collect a CBC with differential and send the results. If this is not possible, patients may be assessed by telephone or email for symptoms.

3.5.4 Follow-Up Visits – Survival/Post-Disease Progression

Once a subject experiences confirmed disease progression or starts a new anti-cancer therapy, the subject moves into the survival follow-up phase and should be contacted (e.g., phone, email, etc.; in-person visit not required) at least every 3 to 6 months to collect information on new anti-cancer treatments received and to assess for survival status until death, withdrawal of consent, or the end of the study, whichever occurs first (see Study Calendar).

3.6 STUDY CALENDAR

Procedure	Screening	Baseline		Study Cycles								Disease Evaluations	End of Treatment and Disease Progression	Post-Treatment Follow-Up		
				C1				C2-6						Safety ¹	Follow-Up (Prior to PD)	Survival (Post-PD)
Scheduling Window (Days):	-28 to -1 ²	-14 ³		5 (-1)	8 (-3)	9	22 (-3)	1 (-3)	8 (-3)	22 (-3)	Every 8 weeks ⁴	Treatment discon/PD ⁵	Day 30 (±7)	Every 60 or 90 days ⁶	Every 3 months ⁷	
Confirmation of Diagnosis ⁸	X															
Physical Exam and ECOG PS ⁹	X	X			X		X	X	X	X		X	X	X		
CBC with Differential	X	X	X		X		X	X	X	X		X	X	X		
Reticulocyte Count	X	X	X		X		X	X	X	X		X	X	X		
Chemistry Panels ¹⁰	X	X	X		X		X	X	X	X		X	X	X		
LDH, Serum Lipase and Amylase	X	X	X		X		X	X	X	X		X	X	X		
Uric Acid, Total Protein		X	X		X		X	X	X	X						
PT/INR and aPTT	X	X	X				X					X	X	X		
Thyroid Function (TSH, reflex free T4)	X	X	X				X					X	X	X		
Urinalysis	X	X	X				X					X				
Pregnancy Test (urine/serum; WOCCBP)	X	X	X													
Hepatitis B and C, HIV Antibody, HTLV-1/2	X															
HLA typing (A, B, C, DR, DQ)		X	X													
Anti-nuclear antibody (ANA), rheumatoid factor (RF) and anti-thyroid antibody	X	X														
Clonal T-cell receptor rearrangement by PCR	X															
Iron panels, Folate, and B12, C-reactive Protein, IL-2R		X	X													
Creatine phosphokinase (CPK), troponin	X	X	X									X		X		

Abbreviated Title: IL-15 and Avelumab in R/R T-cell NHL

Version Date: 09/23/2021

Procedure	Screening	Baseline		Study Cycles								Disease Evaluations	End of Treatment and Disease Progression	Post-Treatment Follow-Up		
				C1				C2-6						Safety ¹	Follow-Up (Prior to PD)	Survival (Post-PD)
Scheduling Window (Days):	-28 to -1 ²	-14 ³		5 (-1)	8 (-3)	9	22 (-3)	1 (-3)	8 (-3)	22 (-3)	Every 8 weeks ⁴	Treatment discon/PD ⁵	Day 30 (+7)	Every 60 or 90 days ⁶	Every 3 months ⁷	
Pulmonary function tests (PFTs) ¹¹	X															
T, B, NK cell subsets		X			X			X	X			X	X	X		
Imaging studies ¹²	X	X										X	X		X	
MRI, Lumbar Puncture ¹³		X										X	X		X	
Bone Marrow Aspiration/Biopsy ¹⁴		X										X	X			
Flow Cytometry ¹⁵		X										X	X	X	X	
Clinical photography and dermatology assessment/ global score ¹⁶		X										X	X		X	
Radiologic Evaluation/ tumor measurement ¹⁷		X										X	X		X	
EKG, TTE	X															
Symptoms/Adverse Events Assessment, Concomitant Medication Review	X	X						X				X	X	X	X	
Research Blood/Tissue Samples ¹⁸		X	X	X	X	X	X	X	X		X	X	X	X		
Survival Status																X

NOTE: Any other tests should be performed as clinically indicated. See Section 3.2 for drug administration information. See Section 5 for information on research blood samples/correlative studies to be collected.

¹ 30 days (± 7) following last dose, and 90 days ($+14$) after last dose of avelumab (via clinic or phone). If initiating new anti-cancer therapy within 30 days after last dose of avelumab, 30-day safety follow-up visit must occur before first dose of new therapy.

² Screening and Baseline evaluations should be performed within 28 days prior to enrollment and dosing, respectively, unless otherwise noted and with the following exceptions: Confirmation of diagnosis (no time limit); HIV antibody, HTLV-1/2 serologies, Hepatitis B surface antigen and Hepatitis C antibody, EKG, and bone marrow aspiration/biopsy (all within 3 months) **NOTE:** Any screening tests performed within the specified time frame for baseline do not need to be repeated.

³ Within 14 days prior to dosing on C1D1, with the following exceptions: Pregnancy test (within 7 days of dosing; must be negative).

⁴ ± 4 days, from date of prior assessment. Confirmatory scans should also be obtained 4 weeks following initial documentation of objective response. After completion of treatment, imaging assessment will be performed at each scheduled post-treatment follow-up visit for up to 3 years.

⁵ To be done at end of treatment (30 days after last dose of study treatment; may be combined with 30 day safety follow-up, if timing coincides). If subject to initiate new anti-cancer therapy assessments should occur before the first dose of the new therapy.

⁶ Follow-up to occur about every 60 days (± 7 days) for first 6 months, every 90 days (± 14 days) for 2 years, then every 6 months (± 28 days) for another 2 years and then annually (± 6 weeks) until disease progression or initiation of new anti-cancer therapy. After completion of treatment, imaging assessment will be performed at each scheduled post-treatment follow-up visit for up to 3 years.

⁷ After disease progression or initiation of new anti-cancer therapy, contact for survival about every 3 to 6 months (± 4 weeks).

⁸ Pathologic review/confirmation of diagnosis by Laboratory of Pathology, NCI (no time limit). If archival sample is not available, a fresh tumor biopsy and/or peripheral blood sample will be obtained.

⁹ Physical exams to include medical history (i.e., complete at Screening/Baseline; interim on study and in follow-up), vitals, weight, and height (screening only). ECOG to be recorded at least once per cycle, on day 1, 8, and/or 22.

¹⁰ Chemistry panels include: Acute care, Hepatic, and Mineral.

¹¹ Diffusing capacity/alveolar volume (DLCO/VA), forced expiratory volume in 1 second (FEV1) for patients with significant pulmonary or smoking history.

¹² At screening a CT scans of neck, chest, abdomen, and pelvis should be performed (with IV and PO contrast, unless patient is allergic or has renal insufficiency; other imaging may be substituted at the discretion of the investigator). Other body areas may be imaged if clinically indicated. MRI of the brain is only required in patients with suspected involvement of CNS. Also, at screening, a FDG-PET/CT torso (extremities to be included if there is confirmed or suspected disease involvement). At baseline one or more of the following studies: CT, MRI, FDG-PET/CT and or clinical photography.

¹³ Patients with neurological symptoms or signs should undergo MRI scan of the brain and lumbar puncture.

¹⁴ Baseline bone marrow aspiration/ biopsy with flow cytometry must be done within 3 months prior to starting treatment. During post-treatment follow-up, repeat bone marrow aspiration/ biopsy needed only to confirm a CR.

¹⁵ Peripheral blood flow cytometry may be done for disease evaluation of patients who had circulating leukemic cells detected at baseline, and for patients with CTCL regardless of their baseline results.

¹⁶ To be performed in selected patients with cutaneous disease (as determined by PI or AI).

¹⁷ Dermatology assessment and Global/mSWAT scoring will be used instead of or in addition to radiologic evaluation for patients with predominantly cutaneous disease

¹⁸ Samples for correlative research are to be collected as indicated in Section 5. Prior biopsy specimen blocks will be used for PD-L1 staining if available. If archival tissue is not available or adequate, baseline punch biopsy of the skin or core needle biopsy of a lymph node/visceral lesion is required, otherwise this is optional.

3.7 COST AND COMPENSATION

3.7.1 Costs

NIH does not bill health insurance companies or participants for any research or related clinical care that participants receive at the NIH Clinical Center. If some tests and procedures performed outside the NIH Clinical Center, participants may have to pay for these costs if they are not covered by insurance company. Medicines that are not part of the study treatment will not be provided or paid for by the NIH Clinical Center.

3.7.2 Compensation

Participants will not be compensated on this study.

3.7.3 Reimbursement

The NCI will cover the costs of some expenses associated with protocol participation. Some of these costs may be paid directly by the NIH and some may be reimbursed to the participant/guardian as appropriate. The amount and form of these payments are determined by the NCI Travel and Lodging Reimbursement Policy.

3.8 CRITERIA FOR REMOVAL FROM PROTOCOL THERAPY AND OFF STUDY CRITERIA

Prior to removal from study, effort must be made to have all patients complete a safety visit approximately 30 days following the last dose of study therapy. Additional safety visits and follow-up will continue as per Section [3.5](#).

3.8.1 Criteria for removal from protocol therapy

Patients who meet the following criteria should be discontinued from protocol therapy:

- Completion of protocol therapy (i.e., up to 6 cycles)
- Confirmed disease progression
- Intercurrent illness that prevents further administration of treatment
- Unacceptable toxicities as listed in Section [3.1.1](#) or those toxicities listed in Section [3.3](#) that require treatment to be stopped
- More than 6 weeks has elapsed since the patient received protocol therapy
- Subject's request to withdraw from protocol therapy
- Investigator's decision to withdraw the patient
- Subject's non-compliance with trial treatment or procedure requirements that requires removal in the opinion of the PI
- Pregnancy
- The drug manufacturer can no longer prove the study agent
- Study is cancelled for any reason

3.8.2 Off-Study Criteria

- Subject requests to be withdrawn from study
- Subject is lost to follow-up
- Death

- Study is cancelled for any reason

3.8.3 Lost to Follow-up

A participant will be considered lost to follow-up if he or she fails to return for two consecutive scheduled visits and is unable to be contacted by the study site staff.

The following actions must be taken if a participant fails to return to the clinic for a required study visit:

- The site will attempt to contact the participant within 3 business days to reschedule the missed visit, and counsel the participant on the importance of maintaining the assigned visit schedule and ascertain if the participant wishes to and/or should continue in the study.
- Before a participant is deemed lost to follow-up, the investigator or designee will make every effort to regain contact with the participant (where possible, 3 telephone calls and, if necessary, a certified letter to the participant's last known mailing address or local equivalent methods). These contact attempts should be documented in the participant's medical record or study file.
- Should the participant continue to be unreachable, he or she will be considered to have withdrawn from the study with a primary reason of lost to follow-up.

4 CONCOMITANT MEDICATIONS/MEASURES

Medications or vaccinations specifically prohibited in the exclusion criteria are not allowed during the ongoing trial, with the exception of oral or parenteral steroids if they are administered more than 7 days before the start of or more than 7 days after the end of IL-15 infusion (Note: Dexamethasone for treatment or prophylaxis of avelumab-associated infusion reactions may be administered at any time). If there is a clinical indication for a prohibited medication/ measure during the trial, discontinuation from trial therapy may be required.

For premedication and supportive care measures, see Section [3.2.1](#), [3.2.2](#) and [3.2.3](#).

4.1 ACCEPTABLE MEDICATIONS

All treatments that the investigator considers necessary for a subject's welfare may be administered at the discretion of the investigator in keeping with the community standards of medical care. All concomitant medication will be recorded on the case report form (CRF) including all prescription, over-the-counter (OTC), herbal supplements, and IV medications. If changes occur during the trial period, documentation of drug dosage, frequency, route, and date may also be included on the CRF.

All concomitant medications received within 28 days before the first dose of trial treatment and 30 days after the last dose of trial treatment should be recorded.

4.2 PROHIBITED MEDICATIONS

Patients are prohibited from receiving the following therapies during treatment on this trial:

- Other therapy for the disease under study not specified in this protocol, unless specifically noted as permitted
- Investigational agents other than rhIL-15 and avelumab
- Radiation therapy

NOTE: Radiation therapy to a symptomatic solitary lesion may be allowed at the investigator's discretion.

- Live vaccines within 30 days prior to the first dose of trial treatment and while participating in the trial. Examples of live vaccines include, but are not limited to, the following: measles, mumps, rubella, varicella/zoster, yellow fever, rabies, BCG, typhoid vaccine and FluMist.

Patients who, in the assessment by the investigator, require the use of any of the aforementioned treatments for clinical management should be removed from the study treatment. Patients may receive other medications that the investigator deems to be medically necessary.

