6.3.2 Response Criteria for PTCL and ALCL

RECIL 2017 criteria (52) use the Deauville five-point scale for assessment of response via FDG-PET. The five-point scale (5-PS) has been validated for use at interim staging and at the end of treatment and was adopted as the preferred reporting method at the First International Workshop on PET in Lymphoma in Deauville, France (i.e., Deauville criteria), and in several international trials.

The 5-PS PS scores the most intense uptake in a site of initial disease:

1. if present, as follows: no uptake or no residual uptake (when used at interim)
2. slight uptake, but below blood pool (mediastinum)
3. uptake above mediastinal, but below or equal to uptake in the liver
4. uptake slightly to moderately higher than liver
5. markedly increased uptake or any new lesion (on response evaluation)

The sum of longest diameter (SLD) is used for assessment of tumor burden. In patients with disseminated disease, a maximum of three target lesions should be selected and used to estimate tumor response. Target lesions should be selected from those with the largest size that can be reproducibly measured and preferably representing multiple sites and/organs. In most cases, lymph nodes can be considered target lesions if the lymph node longest diameter measures ≥ 15 mm. A lymph node measuring between 10 and 14 mm is considered abnormal but should not be selected as a target lesion. Lymph nodes measuring <10 mm in diameter are considered normal. In certain anatomical sites (inguinal, axillary, and portocaval), normal lymph nodes may exist in a narrow, elongated form, and such nodes should not be selected as target lesions if alternatives are available. Extranodal lesions are selected as target lesions if they have soft tissue component, based on their size, and the ease of reproducibility of repeated measurements, with a minimum measurement of the longest diameter of ≥ 15 mm. All other lesions should be identified as nontarget lesions and should be recorded at baseline, without the need to measure them. Nontarget lesions should be followed and reported as present, absent, or clear progression.

Table 14: Response categories based on assessment of target lesions

% Change in sum of diameters of target lesions from nadir					
	CR	PR	MR	SD	PD

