% change from baseline	
 • Complete disappearance of all target lesions and all nodes with long axis <10 mm • $\geq 30\%$ decrease in the sum of longest diameters of target lesions (PR) with normalization of FDG-PET 	$\geq 30\%$ decrease in the sum of longest diameters of target lesions but not a CR	$\geq 10\%$ decrease in the sum of longest diameters of target lesions but not a PR ($<30\%$)	$<10\%$ decrease or $\leq 20\%$ increase in the sum of longest diameters of target lesions	
 • $>20\%$ increase in the sum of longest diameters of target lesions • For small lymph nodes measuring <15 mm post therapy, a minimum absolute increase of 5 mm and the long diameter should exceed 15 mm • Appearance of a new lesion
FDG-PET	Normalization of FDG-PET (Deauville score 1-3)	Positive (Deauville score 4-5)	Any	Any	Any
Bone marrow involvement	Not involved	Any	Any	Any	Any
New lesions	No	No	No	No	Yes or No
CR, complete response; CT, computerized tomography; FDG-PET, [18F]2-fluoro-2-deoxy-D-glucose; MR, minor response; PD, progression of disease; PR, partial response; SD, stable disease.					

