6.3.5 Best Overall Response

The best overall response is the best response recorded from the start of the treatment until disease progression/recurrence (taking as reference for progressive disease the smallest measurements recorded since the treatment started). The patient's best response assignment will depend on the achievement of both measurement and confirmation criteria.

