6.3.9 Event-Free Survival

Event-free survival (EFS) is defined as the duration of time from the date of study enrollment until time of disease relapse, disease progression, alternative therapy for lymphoma given (such as radiation), or death, whichever occurs first.

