10 STATISTICAL CONSIDERATIONS

10.1 STATISTICAL HYPOTHESIS

- Primary Endpoint(s):

- Maximum tolerated dose (MTD) of rhIL-15 administered intravenously for 5 days in combination with avelumab for up to 6 cycles
- Frequency (number and percentage) of treatment-emergent AEs
- Secondary Endpoint(s):
 - Overall response rate (including CR and PR)
 - Overall response rate in patients with $\geq 50\%$ PD-L1-expressing tumor cells
 - Duration of response
 - Progression-free, event-free, and overall survival

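### Radiation to one lesion is permitted on treatment, but the response and DOR rules do not say how that lesion is handled, so its shrinkage can be scored as a PR in a patient who stays on treatment

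*Combined protocol and SAP*

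**What the plan says.** All references are to the combined protocol and SAP.

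- **Radiation on study (4.2).** Radiation is on the prohibited list, with a note beneath it: "Radiation therapy to a symptomatic solitary lesion may be allowed at the" investigator's discretion. The section closes by saying that patients who "require the use of any of the aforementioned treatments for clinical management should be removed from the study treatment". It does not say whether radiation given under the note falls within that sentence. The introduction to Section 4 says only that stopping trial therapy may be required when a prohibited measure is needed.
- **Response endpoint (10.1).** The first secondary endpoint listed is "Overall response rate (including CR and PR").
- **Target lesions (6.3.2).** For lymphoma other than CTCL, "a maximum of three target lesions should be selected and used to estimate tumor response". Table 14 sets PR at a 30% or greater "decrease in the sum of longest diameters of target lesions but not a CR". No text addresses a lesion irradiated on study.
- **Best response (6.3.5).** "The best overall response is the best response recorded from the start of the treatment until disease progression/recurrence". The window does not close at radiation.
- **Evaluable set (10.3.2).** It requires measurable disease, at least one cycle and a re-evaluation. Radiation is not a ground for exclusion.
- **DOR (6.3.6)** ends at progression or recurrence, death or, without progression, the last assessment. Radiation is not mentioned.
- **EFS (6.3.9)** counts as an event "alternative therapy for lymphoma given (such as radiation").
- **Follow-up (3.5, 3.5.3, 3.5.4).** Disease follow-up gives way to survival contact once a new anti-cancer therapy starts. Whether radiation allowed under the note is such a therapy is not stated.

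**The concern.** The plan recognises radiation as a lymphoma treatment for one endpoint and is silent on it for response and DOR. If a patient is irradiated and remains on treatment, the 8-weekly disease evaluations continue. The irradiated lesion stays in the sum of diameters, and any fall is read as an effect of rhIL-15 plus avelumab. The same radiation could make that patient an EFS failure and an ORR responder.

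ORR is the main activity readout of a small trial, and both the decision to irradiate and the response assessment rest with the investigator. Without a written rule, the choice would be made case by case after the scans are known. ORR is also reported by diagnosis and by PD-L1 level (10.1, 10.4.7), where denominators are smaller still.

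**Working it through.** **Inputs.** PR threshold 30% and at most three targets (6.3.2, Table 14). One measurable lesion is enough for entry (2.1.1.4). 9 patients at the MTD, at most 27 evaluable, accrual ceiling 30 (10.2). 95% Agresti-Coull interval (10.4.1). No expected rate of on-study radiation is given.

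**1. The plan's own denominators.** Maximum evaluable: 3 × 6 + 9 = 27. Minimum: 3 × 3 + 9 = 18. Both agree with Section 10.2.

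**2. Local shrinkage needed for a PR.** Let w be the irradiated lesion's share of the baseline sum of diameters. If the other targets do not change and no new lesion appears, the shrinkage needed in that lesion is s = 0.30 / w.

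| Targets | w | s |
|---|---|---|
| Irradiated lesion is the only target | 1 | 30% |
| One of two equal targets | 1/2 | 60% |
| One of three equal targets | 1/3 | 90% |
| Largest of 40, 20 and 15 mm (assumed sizes) | 40/75 = 0.533 | 56% |

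Complete disappearance of one of three equal lesions lowers the sum by 1/3 = 33.3%, which also exceeds 30%.

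**3. Do the other criteria prevent this?** Table 14 asks that there be no new lesion, which local radiation does not affect. The confirmatory scan 4 weeks after a first response (3.6, footnote 4) would repeat the finding but cannot separate a radiation effect from a drug effect. If the irradiated lesion is the only site, FDG-PET normalises and marrow is not involved, Table 14 places a 30% fall under CR.

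**4. Size per response.** 1/9 = 11.1 points; 1/27 = 3.7 points; 1/30 = 3.3 points. Illustrations of removing one such response (responder counts are assumptions):

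| N | With it | Without it |
|---|---|---|
| 9 | 2/9 = 22.2% (5.3 to 55.7) | 1/9 = 11.1% (0 to 45.7) |
| 9 | 1/9 = 11.1% (0 to 45.7) | 0/9 = 0% (0 to 34.5) |
| 27 | 6/27 = 22.2% (10.3 to 41.1) | 5/27 = 18.5% (7.7 to 37.2) |

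**5. Who is exposed.**

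- If radiation under the note counts as new anti-cancer therapy, 3.5 and 3.5.4 move the patient to survival contact, and later disease assessments should not arise.
- If it does not count as such and the patient stays on treatment, scans continue every 8 weeks and steps 2 to 4 apply.
- Removal from study treatment alone does not close the best-response window in 6.3.5, but it makes the first route more likely.

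The gap is therefore mainly the patient irradiated under the note who remains on treatment.

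**6. CTCL.** Skin response uses whole-body mSWAT with a 50% threshold, and a global response requires at least a skin PR (6.3.3). One irradiated lesion matters little unless it dominates the score. Section 6.3.3 also uses the off-treatment date for TTP and DOR, which limits DOR if the patient leaves treatment but does not decide whether a response is scored.

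**The case against.** The strongest reply is that silence is not a rule. A reader might infer that the plan counts irradiated lesions toward response; no sentence says so. Response is assessed by cited published criteria, of which the protocol reproduces only part. Whether those sources deal with irradiated lesions cannot be checked from the documents. This stands as a limit on the wording: the point is that the rules as written permit the scoring. If the source does contain a rule, the protocol should state it.

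A reader might also infer that response, DOR and PFS all run on after radiation in every patient. Sections 3.5, 3.5.3 and 3.5.4 do not support that, since they end disease follow-up at new anti-cancer therapy. That part of the objection stands and narrows the gap. Nor does PFS need repeating with radiation as an event: EFS has the same start and events as PFS plus alternative therapy, and it is already planned.

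It is tempting to call Section 4.2 a flat contradiction. The note can be read as an exception to the bullet above it, outside the removal sentence. The text does not settle this, so it needs reconciling.

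A blanket fix also has costs. Dropping every later assessment would discard genuine responses in lesions that were not irradiated. Censoring DOR just before radiation given for symptoms may be informative and lengthen apparent DOR. Both objections stand and shape the remedy.

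Finally, ORR is descriptive, with no test or go/no-go threshold, and its interval at N = 9 is wide in any case. That limits the weight of the point but does not make the attribution right.

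**Conclusion.** The concern holds in a limited form. For a patient irradiated under the note in 4.2 who stays on treatment, the rules as written can score radiation shrinkage as a PR: 30% of a sole target, 60% of one of two equal targets, 90% of one of three. These figures assume that the other targets are unchanged and no new lesion appears. DOR would then keep running with no rule for radiation.

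Each such response adds 11.1 ORR points at N = 9 or 3.7 at N = 27. The total effect cannot be estimated because no frequency of radiation is given. The effect is diluted in CTCL. The MTD, dose escalation and sample size are unaffected.

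**What to change.** In Sections 6.3 and 10.4.3:

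- **Lesion.** State that a lesion irradiated on study is not evaluable for response from the date of radiation.
- **ORR.** A CR or PR first documented after radiation does not count in the main ORR if it depends on that lesion, which is always so when it is the only target. Say how dependence is judged, for example by recomputing the sum with that lesion left out at baseline and follow-up. Keep the patient in the denominator and list all such patients.
- **Sensitivity analysis.** Report ORR with all post-radiation assessments excluded.
- **DOR.** State one rule for radiation. Report the result both censored at the last assessment before radiation and with radiation counted as an event, as in EFS.
- **PFS.** No change; EFS already gives the companion analysis.

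Separately, the sponsor must reconcile the note and the removal sentence in 4.2 with the introduction to Section 4 and the follow-up rules in 3.5, 3.5.3 and 3.5.4, including whether permitted radiation is a new anti-cancer therapy. This review does not say which should govern.

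**Cost:** a few sentences and one extra listing. ORR may be slightly lower, and a few patients may become non-evaluable at the irradiated site. Recruitment and planned N do not change.
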